12. EVALUATION OF ADVERSE EVENTS AND SAFETY INFORMATION

12.1. DEFINITIONS

12.1.1. Adverse Event

An Adverse Event (AE) is any untoward medical occurrence in a patient or clinical investigation subject who is administered a medicinal product and which does not necessarily have a causal relationship with this treatment. An AE, therefore, can be any unfavorable or unintended sign (including an abnormal laboratory finding), symptom, or disease temporally associated with the use of a medicinal product, whether or not related to the medicinal product.

12.1.2. Adverse Drug Reaction

An Adverse Drug Reaction (ADR) is any noxious and unintended response to an Investigational Medicinal Product (IMP) which is a reasonably likely to have been caused by the drug, at any dose administered. The definition covers also medication errors and uses outside what is foreseen in the protocol, including misuse and abuse of the product. For the purposes of IND safety reporting, “reasonable possibility” means there are facts (evidence) or arguments to suggest a causal relationship between the drug and the adverse event.

12.1.3. Serious Adverse Events

A serious adverse event (SAE) is defined as any adverse experience that, in view of either the Investigator or Sponsor, meets any of the following criteria:

- Results in death.
- Is life-threatening.

NOTE: Life-threatening means that the patient was at immediate risk of death from the reaction as it occurred, i.e., it does not include an event which hypothetically might have caused death had it occurred in a more severe form.

- Requires inpatient hospitalization or prolongation of existing hospitalization.

NOTE: In general, hospitalization means that the individual remained at the hospital or emergency ward for observation and/or treatment (usually involving an overnight stay) that would not have been appropriate in the physician's office or an out-patient setting. Complications that occur during hospitalization are AEs. If a complication prolongs hospitalization or fulfills any other serious criteria, the event is serious. When in doubt as to whether “hospitalization” occurred, the event should be considered serious.

- Results in persistent or significant disability/incapacity or a substantial disruption of a person's ability to conduct normal life functions.

NOTE: This definition is not intended to include experiences of relatively minor medical significance such as uncomplicated headache, nausea, vomiting, diarrhea, influenza, or accidental trauma (e.g., sprained ankle) which may interfere or prevent everyday life functions, but do not constitute a substantial disruption.

- Is a congenital anomaly/birth defect.
- Is an important medical event. *An important medical event is an event that may not result in death, be life-threatening, or require hospitalization but may be considered a SAE when, based upon appropriate medical judgment, it may jeopardize the patient and may require medical or surgical intervention to prevent one of the outcomes listed above. Examples of such medical events include allergic bronchospasm requiring intensive treatment in an emergency room or at home, blood dyscrasias or convulsions that do not result in patient hospitalization, or the development of drug dependency or drug abuse.*

Pre-planned hospitalization or hospitalization for routine treatment or monitoring of the studied indication, not associated with any deterioration in condition are not considered to be SAEs (see Par. 12.4.2). These events must be recorded in the AE page of the CRF where a variable will be ticked to indicate that they are not SAEs.

Death shall always be reported as SAE and a cause of death shall always be specified when known.

12.1.4. Unexpected Adverse Events

An AE or ADR is considered unexpected if it is not listed in the Investigator Brochure (reference safety information) or is not listed at the specificity or severity that has been observed and listed in the Investigator Brochure. Events that are mentioned in the Investigator Brochure as occurring with a class of drugs or as anticipated from the pharmacological properties of the drug, but are not specifically mentioned as occurring with the particular drug under investigation are considered unexpected (21 CFR312.32(a)).

12.1.5 Suspected unexpected serious adverse reaction

A suspected unexpected serious adverse reaction (SUSAR) is defined as an adverse reaction that is both unexpected (not consistent with the applicable product information) and meets the

definition of a Serious Adverse Reaction. The determination of expectedness should be made on the basis of the IB (reference safety information).

12.1.6. Adverse Events of Special Interest (Sight-threatening Events)

The following adverse events are considered to be of special interest and by default are to be reported as SAEs (medically important criteria):

- Adverse Events that cause an unexpectedly severe progression of optic neuropathy as measured by central vision loss (i.e. decrease in visual acuity of >30 ETDRS letters or > +0.6 LogMAR lasting >1 hour compared with the last assessment of visual acuity at the last visit), by visual field testing, or by examination of the optic nerve.
- Adverse Events that cause a decrease in visual acuity to the level of Light Perception or worse lasting >1 hour.
- Adverse Events that require surgical intervention (e.g., conventional surgery, vitreous tap or biopsy with intravitreal injection of anti-infectives, or laser or retinal cryopexy with gas) to prevent permanent loss of sight.
- Adverse Events associated with severe intraocular inflammation (i.e., 4+ anterior chamber cell/flare or 4+ vitritis).
- Adverse Events that, in the opinion of the investigator, may require medical intervention to prevent permanent loss of sight.

During the study all sight threatening events will be considered equivalent to a SAE and will be reported following the procedures described below for the reporting of a SAE.

12.2. MONITORING FOR ADVERSE EVENTS

At each visit following study informed consent form signature, after the patient has had the opportunity to spontaneously mention any problems, the Investigator or appropriate designee should inquire about AEs by asking the standard questions:

- “Have you had any health problems since your last study visit?”
- “Have there been any changes in the medicines you take since your last study visit?”

AEs should be reported for any clinically relevant change in concomitant condition(s) that is the result of an untoward (unfavorable and unintended) change in a patient's medical health. Changes in any protocol-specific ocular or systemic parameter evaluated during the study are to be reviewed by the Investigator. In addition, the patient's responses to any questionnaire utilized during the study are to be reviewed by the Investigator. Any untoward (unfavorable and unintended) change in a protocol-specific parameter or questionnaire response that is clinically

relevant is to be reported as an AE. These clinically relevant changes will be reported regardless of causality.

The Investigator should report information on SAEs that continue after patient has completed his/her participation in the study (whether study completion or withdrawal), unless patient has withdrawn his/her consent.

In line with ICH E2A provisions, although the Investigator does not usually need to actively monitor subjects for adverse events once the trial has ended, if the Investigator becomes aware of a serious adverse event occurring to a subject after the treatment of that subject has ended, the SAE should be reported by the Investigator to the Sponsor. Such “post-study cases” should be regarded for expedited reporting purposes as though they were study reports. Therefore, a causality assessment (by the Investigator and by Dompé) and determination of expectedness (by Dompé) are needed for a decision on whether or not expedited reporting is required.

12.3. RECORDING

Adverse Events: all AEs (non-serious and serious) which occur during the course of the study will be recorded in the eCRF. Any pre-existing medical conditions or signs/symptoms present in a patient prior to the start of the study (i.e., before informed consent is signed), should be entered in the baseline history section of the eCRF of the EDC system. Subsequent to signing an informed consent form, all untoward medical occurrences that occur during the course of the study must be documented on an Adverse Event Form (AEF) in the eCRF of the EDC system. A separate AEF must be filled out for each event. When possible, signs and symptoms indicating a common underlying pathology should be documented as one comprehensive event. For each recorded event, the AE documentation must include the onset date, outcome, resolution date (if event is resolved), intensity (i.e., severity), any action with study treatment taken as a result of the event, and an assessment of the adverse event relationship to the study treatment.

12.3.1. Relationship of AEs to the Investigational Product

The Investigator will assess the relationship between the AE and the investigational medication, according to the criteria in Table below:

**Relationship of the Adverse Event to the IMP**

| | |
|---------------------------|--|
| None (Intercurrent Event) | An event that is not and cannot be related to the investigational product, e.g. patient is a passenger in a road traffic accident or surgical intervention performed during the study, but planned before patient enrolment into the study |
| Unlikely (remote) | Relationship is not likely e.g. a clinical event including laboratory test abnormality with temporal relationship to drug administration which makes a causal relationship improbable and in which other drugs, chemicals or underlying disease provide plausible explanations |
| Possible | Relationship may exist, but could have been produced by the patient's condition or treatment or other cause |
| Probable | Relationship is likely, the AE abates upon discontinuation of investigational product and cannot be due to the patient's condition |
| Highly Probable | Strong relationship, the event abates upon discontinuation of investigational product and, if applicable, re-appears upon repeat exposure |

An ADR is defined as an adverse experience which is reasonably likely to have been caused by the drug. Events considered “Possible”, “Probable” and “Highly Probable” related to the IMP treatment and implying a reasonable possibility, if considered serious and unexpected, will be reported to appropriate regulatory authorities.

12.3.2. Severity of AEs

The Investigator will grade the severity of any AE using the definitions in the Table below. For each episode, the highest severity grade attained should be reported.

Severity of the Adverse Event

| | |
|----------|--|
| Mild | Grade 1 - Does not interfere with patient's usual function (awareness of symptoms or signs, but easily tolerated [acceptable]). |
| Moderate | Grade 2 - Interferes to some extent with patient's usual function (enough discomfort to interfere with usual activity [disturbing]). |
| Severe | Grade 3 - Interferes significantly with patient's usual function (incapacity to work or to do usual activities [unacceptable]) |

12.4 Serious Adverse Event Reporting Procedure (from Investigator to CRO/Dompé)

12.4.1. Reporting Procedure from Investigator to Dompé and CRO

The Investigator must record all SAEs, including sight-threatening events, occurring at any time during the study regardless of presumed causal relationship, on the Serious Adverse Event form in the eCRF of the EDC system within 24 hours of learning of the event; information on the SAE must also be recorded on a specific Non-Carbon Repeat SAE form (included in the Investigator's Site File) and forwarded to CRO Drug Safety and Dompé Drug Safety, within 24 hours from first knowledge, to the following addresses:

- by fax through the e-[contact] (linked to Dompé Drug Safety and to CRO Drug Safety).

- or, via e-mail to all following addresses:

- [contact];
- [contact];
- [contact].

In case of unmasking by the investigator, the investigator will fill in the SAE form and all the other related documents (query template, narrative etc) with only the kit number of the treatment taken by the patient, without disclosing the treatment.

The EDC system will ensure that an automatic email will be generated and sent directly to the Dompé pharmacovigilance, trial management, and CRO accountable to receive the study safety information and to prompt a review of the reported SAE by the Medical Expert.

Follow-up reports (as many as required) should be completed and faxed/e-mailed following the same procedure above, marking the SAE form as “follow up Number XX”.

Whenever more than one SAE is observed, the Investigator should identify which is the primary adverse event, i.e. the most relevant one. If other events are listed in the same report, the Investigator, along with their relatedness to the Investigational Product, should identify which adverse events are serious and which are non-serious. In any case, the Investigator is requested to record his/her opinion about the relatedness of the observed event(s) with the investigational medication.

An assessment of expectedness and causality of each serious adverse event will be performed case by case by Dompé/CRO. For SAE reported by an Investigator as not related that is subsequently revised to be related by Dompé, the Investigator will receive a notification.

12.4.2 Conditions that should not be reported as serious adverse events

The conditions listed below, that may require hospitalization of a patient, are not considered to be SAE and shall not be reported as such, but only need to be recorded in the CRF:

- Hospitalizations planned before entry into the clinical study which is part of the normal treatment or monitoring of the studied indication and not associated with any deterioration in condition.
- Hospitalization for routine treatment or monitoring of the studied indication, not associated with any deterioration in condition.
- Hospitalization for treatments, which was elective or pre-planned, for a pre-existing condition that is unrelated to the indication under study and did not worsen.
- Hospitalization for general care not associated with any deterioration in condition.
- Treatment on an emergency, outpatient basis for an event not fulfilling any of the definitions of SAEs given above and not resulting in hospital admission.

In addition, the following situation shall not be considered SAE:

- Trial end points
- Abnormal lab values or test results that do not induce clinical signs and/or symptoms and require intervention/therapy and that therefore are not clinically significant.

12.4. 3. Expedited Reporting Procedure to IRB and to Regulatory Authorities

In addition to reporting the SAE to Dompé (and the CRO), the Investigator must also comply with the requirements related to the reporting of SAEs to the IRB which approved the study. The requirements of IRBs vary from one IRB to another; however, as a minimum requirement, the Investigators must promptly report all suspected unexpected serious adverse reactions (**SUSAR**) to their IRB.

In line with provisions set forth in 21CFR312, Dompé shall notify all participating Investigators in an IND safety report of any suspected adverse reaction that is both serious and unexpected and of potential serious risks, from clinical trials or any other source, as soon as possible, but in no case later than:

- seven calendar days after becoming aware of the information if the event is fatal or life threatening; to be followed by any relevant information within eight days.

- fifteen calendar days after becoming aware of the information if the event is serious but neither fatal nor life threatening.

The Investigators in turn shall notify their IRB.

If the results of an investigation show that an ADR not initially determined to be reportable is reclassified as reportable, the Sponsor shall report such reaction in a written safety report as soon as possible, but in no event later than 7/15 calendar days after the determination is made.

Considering the number of patients enrolled and that the study is monocentric, to prevent any risk to compromise the integrity of the study, Dompé will notify the Investigator in a blinded fashion of any SUSAR (determined by the Sponsor as related).

Copies of all correspondence relating to reporting of any SUSARs to the IRB should be maintained in the Investigator's Files.

Dompé shall also notify FDA in an IND safety report of potential serious risks, from clinical trials or any other source, as soon as possible after Dompé determines that the information qualifies for reporting, in particular shall notify of:

- any suspected adverse reaction that is both serious and unexpected. Dompé must report an adverse event as a suspected adverse reaction only if there is evidence to suggest a causal relationship between the drug and the adverse event.
- findings from other studies that suggest a significant risk in humans exposed to the drug. Such a finding would result in a safety-related change in the overall conduct of the clinical investigation.
- findings from animal or in vitro testing that suggest a significant risk in humans exposed to the drug
- increased rate of occurrence of serious suspected adverse reactions.

Treatment will be unmasked by Sponsor Pharmacovigilance prior to submission of a SUSAR to Regulatory Authorities and only cases referred to active treatment will be considered expeditable for regulatory reporting, in line with law requirements.

12.4.4.. Periodical Reporting to Regulatory Authorities

Dompé shall be responsible to prepare and submit annual safety reports (Development Safety Update Report – DSUR) to relevant Regulatory Authorities.

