For non-sexually active females, abstinence may be regarded as an adequate method of birth control; however, if the patient becomes heterosexually active during the study treatment period, she must agree to use adequate birth control methods as defined above for the remainder of the study treatment period.

Pregnancy should be avoided in patients or partners during the first month after completing the treatment with the Investigational Product.

| | |
|-----------------------------|--|
| Assessments: | Safety 
 • Adverse events • Best corrected distance visual acuity (BCDVA) • Intraocular pressure (IOP) • Slit lamp examination (SLE) • External ocular examination • Humphrey Visual Field 24-2 or 10-2 • Dilated fundus ophthalmoscopy • Ocular Coherence Tomography (OCT) • Mitochondrial redox potential • Electroretinogram (ERG) • Ocular tolerability using visual analogue scale (VAS) |
| Endpoints | Safety Endpoints: Safety will be assessed by the following outcomes (occurrence of these outcomes does not necessarily require cessation of therapy): 
 • Unexpectedly severe progression of optic neuropathy as measured by central vision loss, by visual field testing, or by examination of the optic nerve. • Intolerance or allergy to the drug. • Adverse events affecting ocular function or eye pressure, which differ from those expected in the course of glaucoma, which are thought to be potentially related to the drug. • Local or systemic toxicities considered serious adverse events that are potentially related to the drug. Elevation of intraocular pressure, although not seen previously in human use and not expected in this population, will be considered for cessation of therapy in patients with glaucoma. Data on all adverse events will be collected regardless of severity or potential relationship to the drug. Tolerability will be assessed through a Visual Analog Scale (VAS) |
| Sample size: | As the objectives of this study are to evaluate the safety and explore the biological effects of a single rhNGF dosage, sample size was calculated based on clinical feasibility and no formal sample size calculation has been performed. Proposed sample size is of 60 patients adequate to make appropriate estimation of study variables. |

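### Protocol 12.4.2 exempts trial endpoints from SAE status without limit, while 12.1.6 and 12.4.1 make adverse events causing the first safety endpoint SAEs reportable within 24 hours

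*Protocol*

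**What the plan says.** Protocol 12.4.2 lists what is not to be reported as an SAE. After several types of hospitalization and outpatient treatment it adds "In addition, the following situation shall not be considered SAE". The first bullet under that sentence is "Trial end points" and nothing more.

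The Synopsis lists four safety endpoints. The first is "Unexpectedly severe progression of optic neuropathy as measured by central vision loss, by visual field testing, or by examination of the optic nerve". The fourth is "Local or systemic toxicities considered serious adverse events that are potentially related to the drug". SAP 3.4 adopts all four as primary safety outcomes.

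Protocol 12.1.6 opens its list of adverse events of special interest (AESIs) with "The following adverse events are considered to be of special interest and by default are to be reported as SAEs (medically important criteria)". The first entry is an adverse event causing the progression named in the first endpoint. The section closes by saying that "all sight threatening events will be considered equivalent to a SAE and will be reported following the procedures described below".

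Protocol 12.4.1 then says "The Investigator must record all SAEs, including sight-threatening events, occurring at any time during the study regardless of presumed causal relationship", with a 24-hour limit from learning of the event. It adds that "An assessment of expectedness and causality of each serious adverse event will be performed case by case" by the sponsor or CRO.

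**The concern.** For the event this trial most needs to detect, the protocol gives two opposite instructions on whether it is an SAE. Safety and tolerability are the primary objective, and the Introduction says there are no data on rhNGF in patients with a history of raised intraocular pressure and progressive optic nerve disease.

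If a site applied 12.4.2, two things could go wrong:

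- **Reporting.** The event could miss the 24-hour report and the case-by-case assessment in 12.4.1. Later steps depend on that report. The 7- and 15-day clocks in 12.4.3 start when the sponsor becomes aware, and the SUSAR unmasking in 12.5 refers to an SAE that has been reported.
- **Analysis.** The SAP takes SAE and AESI status from what the site enters on the adverse event form, so the event could be missing from those counts.

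**Working it through.** No sample-size or power figure is involved. The check compares the passages and then traces the effect to the outputs.

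**1. The rules side by side**, for an adverse event causing unexpectedly severe optic-neuropathy progression:

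| Section | Status | Limit or exception stated |
|---|---|---|
| Protocol 12.1.6 | SAE by default | none for endpoints |
| Protocol 12.4.1 | SAE, report in 24 hours | none for endpoints |
| Protocol 12.4.2 | not an SAE, if it is a trial endpoint | none for 12.1.6 events |
| SAP 7.2.10 | every AESI is an SAE | none for endpoints |

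No passage ranks these rules. Protocol 12.1.3 refers to 12.4.2, but only for hospitalizations. Every other item in 12.4.2 carries a limiting condition, such as no deterioration or no clinical significance. The endpoint bullet has none.

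**2. Can the bullet be literal?** No. Protocol 11.5.4 names adverse events as the primary safety endpoint. A literal exemption of endpoints would then remove SAE status from every event.

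**3. Does it mean efficacy endpoints only?** Possibly, but it does not say so, and that limit would not be enough by itself. Change in BCDVA is an efficacy variable in 11.5.5, and a fall of more than 30 ETDRS letters is one of the measures of central vision loss in 12.1.6.

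**4. The fourth endpoint.** It is defined by being considered an SAE, so exempting it from SAE status is circular. This is a wording defect, not a second competing reporting rule.

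**5. Effect on the outputs.** SAP 7.2.10 counts an event as serious if the seriousness question is answered yes or left blank. It identifies AESIs from the medically-important box in the SAE criteria section. A no answer removes the event from the SAE counts, and an unticked box removes it from the AESI count. Outputs that could change:

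- four rows of Table 14.3.1-01.1: Serious AEs, Serious TEAEs, Treatment Related Serious TEAEs, AESIs;
- Table 14.3.1-07.1 (serious TEAEs by SOC and PT);
- Listing 16.2.11-5.1 (serious AEs);
- in Table 14.2-1.1, local toxicities and systemic toxicities. These are two of the six incidences in SAP 10.6.1; the others are optic-neuropathy progression overall, the same during treatment, intolerance or allergy, and unexpected related AEs affecting ocular function or pressure.

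The two optic-neuropathy incidences do not change. SAP 7.2.7 takes them from per-eye tick boxes on the BCDVA, visual field, ERG and OCT pages.

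**6. Size per missed event.** Each missed event lowers an event count by 1. The patient count in a row falls only if the missed event was that patient's only qualifying event for the row. Assuming all 60 planned patients are treated, 40 and 20 per arm:

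- rhNGF: 1/40 = 2.5 percentage points;
- vehicle: 1/20 = 5.0 percentage points.

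**The case against.** **The endpoint is not the adverse event.** The Synopsis endpoint is the progression, while 12.1.6 concerns adverse events that cause it, and the SAP captures the two separately. On this view 12.4.2 says only that reaching an endpoint does not by itself create an SAE. This does not hold in practice: 11.5.4 and 12.2 require any clinically relevant untoward change in a study parameter to be reported as an adverse event, so both descriptions cover the same occurrence.

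**The specific rule is clear and repeated.** Protocol 12.1.6 and 12.4.1 and SAP 7.2.10 all point one way against a three-word bullet whose literal reading is absurd. This stands as a forecast: a site would probably report the event. It is not a rule of precedence, and 12.4.2 is itself a specific list of exceptions.

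**Section 11.5.5 lists group summaries of BCDVA change, not one patient's loss.** True, but those summaries are made of individual changes, and a site deciding on one patient could read the bullet either way.

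**The reach is limited.** This largely stands. All AEs still go into the eCRF (12.3), and an event marked non-serious still appears in the general AE tables. A blank seriousness answer counts as serious. The sponsor may itself class an event as serious (12.1.3), although no time limit is set for that. The toxicity outcomes come from their own question on the adverse event form, whose wording is not in the documents, so those rows could change but need not. The systemic row is reached only through the circular fourth endpoint. The 1/40 and 1/20 figures apply to any misclassified patient and say nothing about frequency.

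**Conclusion.** The concern holds. As written, 12.4.2 denies SAE status to an event that 12.1.6 and 12.4.1 make an SAE with 24-hour reporting, and no passage settles which applies. One of the four listed safety endpoints is in direct conflict, and a second is circular.

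The harm is conditional on a site following 12.4.2, and its frequency cannot be estimated because the documents give no expected event rate. If it happened, the consequences would be a late or missing expedited report and understated SAE and AESI counts, by the amounts shown above. The percentages rest on a Safety Set of 40 and 20. This should be fixed because safety is the primary objective, but it does not undermine the optic-neuropathy outcome.

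**What to change.** Reconcile the passages by protocol amendment, in one of two ways:

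- delete the trial-endpoints bullet from 12.4.2; or
- restrict it to the efficacy variables of 11.5.5 and state that any event meeting 12.1.3 or 12.1.6 is reported under 12.4.1 even if it is also a trial endpoint.

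The second option needs both parts, because BCDVA change belongs to both 11.5.5 and 12.1.6. The SAP needs no change, since 7.2.10 already treats every AESI as an SAE.

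The cost is a short amendment at a single site, with the approvals that Protocol section 6 requires. SAP 3.6 shows that the study has also used a protocol clarification letter; whether one would satisfy section 6 here is for the sponsor to confirm. There is no cost to data or power, and no treatment rule changes.
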